## Study Procedures & Statistical Analysis Plan

Recruitment: Patients will be recruited for the 4-week proof-of-concept trial from the South Florida Behavioral Health Network in Miami, FL. A targeted educational and recruitment in-service meeting will be conducted with the participating South Florida Behavioral Health Network opioid treatment program site, as facilitated by the President/CEO. The goal of the in-service meeting will be to make providers and clinical administrators aware of this project, and to assist in identifying eligible participants. Providers and administrators at the site will be informed about the purpose, procedures, risks, and benefits of the protocol, as well as the inclusion and exclusion criteria, so that they can best discuss the research project with individual staff and patients that might be eligible and interested, and make appropriate referrals to the research team for study inclusion.

Participants will be recruited by designated site staff under the direction of the PI. Treatment center intake staff will identify potential participants based on study inclusion/exclusion criteria and refer to research staff to confirm eligibility and enroll in the trial. Treatment staff will be made aware that participants must be  $>18$  years of age, own a smartphone, have a primary DSM-5 opioid use disorder diagnosis, be receiving buprenorphine, and cannot have any severe mental illness (e.g., schizophrenia) or other condition that would preclude them from participating. Research staff will conduct a second layer of verification (following referral from treatment staff) to ensure all participants are eligible and able to fully participate. To aid in recruitment and retention, all participants will be compensated for their time (see *Procedures* sections below for more information regarding compensation amount). Once participants are actively enrolled in the 4-week pilot study, research staff will maintain at least weekly personal contact with participants. The research team has relevant experience working with addictions treatment populations, and efficiently performing recruitment, screening, and follow-up to maintain participant flow and high follow-up rates. Recruitment and retention tracking will be reviewed on weekly study team conference calls so that potential recruitment shortfalls can be identified proactively and recruitment efforts broadened.

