Procedures: A 4-week, randomized proof-of-concept pilot study will assess the feasibility, acceptability, and effectiveness of the PROCare Recovery app. Participating providers will be trained on the PROCare app prior to enrolling patients. Eligible patients will complete an electronic informed consent form prior to enrollment in the trial. Participants will complete baseline measures of study outcomes. Patients will be oriented to the app at the outset of treatment during the induction phase and continued throughout the 4-week trial. Remote patient outcomes data will be collected during treatment and at the end of the study via the PROCare app, which will include the same measures completed at baseline. Following 4-week participation, patients will be contacted to provide qualitative/quantitative feedback on PROCare usability.

Primary outcomes (and established endpoints) include rates of: buprenorphine adherence ( $>90\%$  daily doses [14]), care plan adherence ( $>50\%$  of weekly care plan activities [54]), and participation in daily outcomes monitoring surveys ( $>90\%$  [45]) using a combination of patient/provider self-report and verification via app/dashboard, clinic UDS results, and GPS location tracking data (to confirm attendance at outpatient appointments). Pre/post change in the secondary outcomes will be assessed using validated measures: opioid/other substance use (days of use), craving (Opioid Craving Scale [63]), motivation (Readiness Ruler [64, 65]), self-efficacy (Brief Situational Confidence Questionnaire [70]), quality of life (WHO EUROHIS Quality of Life Scale [66]), DSM-5 OUD diagnostic criteria [71], depression (Patient Health Questionnaire-9 [PHQ-9])/anxiety (General Anxiety Disorder-7 [GAD-7]). The System Usability

Scale [72] will be used to objectively quantify the usability of the PROCare prototype using a naive sample (Aim 2 sample is distinct from Aim 1 sample). Participants assigned to the PROCare group will also be asked to complete ultra-brief daily check-in measures. Additional information collected from PROCare participants will include activity data within the app (e.g., clicks, timing). Pre/Post data will be entered into a web form on tablet, laptop, or mobile device, and immediately sent (and stored), item-by-item, to the cloud platform that is hosted in a HIPAA secure physical and software environment. The entered data is visible to the participant in the screen of the device at that time, but is not stored locally.

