
Participants in both conditions (PROCare and treatment as usual/control) will receive \$50 for their study participation. As stated in the consent form, participants will only receive the \$50 gift card after they complete the 4-week follow-up. In order to receive the \$50, the participant must complete both the baseline and follow-up measures. Patients allocated to the PROCare group will have the opportunity to earn an additional \$150 in monetary incentives over the course of the 4-week trial based on their level of participation in various activities using the app (competing brief daily check-in surveys, reading psychoeducational materials in the content library, answering questions about adherence to their buprenorphine medication, attending treatment appointments, etc.). Participants in the PROCare group will receive monetary incentives using a smart debit card (*True Link*), which has a feature that can block purchases from certain vendors (liquor stores, etc.) and also block cash withdrawals. True Link smart debit cards have been used to good effect in numerous addiction treatment settings and similar reward-based research studies, and represent the most feasible option relative to cash payments. Due to randomization, participants will have an equal chance of being allocated to the PROCare group and having the opportunity to earn additional incentives. The amount of additional incentives for completing various activities within the app (\$150) is consistent with other similar reward-based substance use disorder apps.

**Statistical Analysis Plan:** Consistent with best practice guidelines for pilot trial sample size calculations with a medium effect size [73, 74] the proposed pilot study will attempt to include a minimum of 15 participants per arm. Accounting for an expected 30% attrition rate, we will attempt to recruit 40 patients. Independent samples t-tests and Pearson's chi-squared tests will determine mean differences on continuous and dichotomous variables, respectively.

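### The continuous secondary outcomes are measured at baseline and at 4 weeks, but no analysis adjusting for baseline as a covariate is planned

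*Combined protocol and SAP*

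**What the plan says.** Everything on this point is in the combined protocol and SAP, under "Study Procedures & Statistical Analysis Plan".

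- **Measurement.** The Procedures text states: "Participants will complete baseline measures of study outcomes". It describes the end-of-study collection as one "which will include the same measures completed at baseline". Payment in both arms depends on this, since "the participant must complete both the baseline and follow-up measures".
- **Form of the secondary outcomes.** "Pre/post change in the secondary outcomes will be assessed using validated measures". The list covers days of use, craving, motivation, self-efficacy, quality of life, DSM-5 OUD criteria, PHQ-9 and GAD-7.
- **Analysis.** "Independent samples t-tests and Pearson's chi-squared tests will determine mean differences on continuous and dichotomous variables, respectively". No covariate, regression, ANCOVA or mixed model is named anywhere.
- **Size.** "the proposed pilot study will attempt to include a minimum of 15 participants per arm" and "Accounting for an expected 30% attrition rate, we will attempt to recruit 40 patients".

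The plan does not state whether the t-test is run on change or on the 4-week score, or whether DSM-5 OUD criteria will be a symptom count or a yes/no diagnosis.

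**The concern.** A change score uses the baseline value with its coefficient fixed at 1. When the correlation r between baseline and follow-up is below 1 and the SDs are equal, that coefficient is too large. If the arms differ at baseline by chance, the change score over-corrects by (1 − r) times the difference, so the estimate carries part of the imbalance with its sign reversed. The fixed coefficient also adds noise. ANCOVA estimates the coefficient from the data and avoids both problems on average.

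This matters because a small pilot is read mainly through its estimates and intervals. With seven clearly continuous secondary measures and about 14 or 15 patients per arm, a visible baseline imbalance on at least one is likely. If no adjusted model is named beforehand, whether to adjust will be decided after the data are seen.

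**Working it through.** **Inputs from the plan.** Minimum 15 per arm, 30% attrition, 40 recruited, equal chance of allocation.

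**Assumed, because the documents give no value.** Two-sided alpha 0.05; normal scores with SD 1 at both times; r = 0.3, 0.5 or 0.7; an effect of d = 0.5 (the plan mentions a medium effect without a number).

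**1. The plan's recruitment figure.** 15 per arm is 30 in total. Dividing by 0.7 gives 42.9, so 43. Multiplying by 1.3 gives 19.5 per arm, rounded up to 20, so 40. The stated 40 therefore matches multiplication. It leaves 40 × 0.7 = 28 completers, or 14 per arm. Both 14 and 15 are shown below; this shortfall is a separate matter.

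**2. Variance of the arm difference**, in units of 2·SD²/n, with N the total analysed:

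- 4-week score only: 1
- change score: 2(1 − r)
- ANCOVA: (1 − r²)(1 + 1/(N − 4)), where the last factor is the cost of estimating the slope (25/24 at N = 28)

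The ANCOVA/change ratio is (1 + r)/2 × 25/24 = 0.677 / 0.781 / 0.885 at r = 0.3 / 0.5 / 0.7. ANCOVA on 28 patients is thus as precise as the change score on 28/0.677 = 41, 28/0.781 = 36 or 28/0.885 = 32.

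**3. Break-even.** Setting (1 + r)/2 × 25/24 = 1 gives r = 0.92 at N = 28. With 27/26 at N = 30, r = 0.926.

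**4. Interval width and power.** Simulated, with 2,000,000 null trials per setting for width and 500,000 at d = 0.5 for power.

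| | r = 0.3 | r = 0.5 | r = 0.7 |
|---|---|---|---|
| Mean 95% CI width (SD), 14 per arm: change v ANCOVA | 1.82 v 1.50 | 1.54 v 1.36 | 1.19 v 1.12 |
| Narrowing, 14 per arm | 17.6% | 11.5% | 5.8% |
| Mean 95% CI width (SD), 15 per arm | 1.75 v 1.44 | 1.48 v 1.31 | 1.15 v 1.08 |
| Power, 14 per arm | 19% v 26% | 25% v 30% | 38% v 42% |
| Power, 15 per arm | 20% v 28% | 26% v 32% | 40% v 44% |

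At r = 0.9 and 14 per arm the widths are 0.688 v 0.686, so the gain has almost gone.

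**5. Chance imbalance.** The SD of the baseline difference is √(2/14) = 0.378, so a difference above 0.5 SD in either direction has probability 0.186. At 15 per arm the figures are 0.365 and 0.171. For a difference of exactly 0.5 SD the change-score error is −(1 − r) × 0.5 = −0.35 / −0.25 / −0.15 SD; for ANCOVA it is 0 on average.

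**6. False positives for the change score, 14 per arm.** In the 19% of trials with imbalance above 0.5 SD: 13.4 / 11.1 / 8.7%. In the other 81%: 3.1 / 3.6 / 4.2%. Weighted at r = 0.3: 0.186 × 13.4 + 0.814 × 3.1 = 5.0%. The overall rate is also 5.0% at the other two values of r. ANCOVA is 4.9 to 5.1% in both groups.

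**7. If the t-test is on 4-week scores instead.** The mean width at 14 per arm is about 1.54 whatever r is, against 1.50 / 1.36 / 1.12 for ANCOVA, so intervals narrow by about 3% / 12% / 27%. ANCOVA wins when (1 − r²) × 25/24 < 1, that is, r above 0.20. The imbalance error is then +r times the imbalance, in the same direction as the imbalance.

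**The case against.** **The change-score reading is inferred.** This stands. On the other reading the gain rises with r instead of falling, and the imbalance error has the opposite sign. The recommendation does not change: at 28 completers and equal SDs, ANCOVA is more precise than both alternatives for r from about 0.20 to 0.92.

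**A change score already uses baseline.** Correct. What is missing is a covariate-adjusted estimate.

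**The 0.92 threshold and the (1 − r) error need equal SDs.** Also correct. In general the over-correction factor is 1 − r × (follow-up SD / baseline SD). If the baseline SD were 0.8 of the follow-up SD, the change score would be at least as precise at N = 28 for r of about 0.64 to 0.89; at 0.7 of it, for about 0.53 to 0.82. Its advantage there is at most about 4% in variance, so the possible loss from ANCOVA is small. If the follow-up SD is the smaller one, ANCOVA gains more.

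**The conditional error rates make a valid test look bad.** They describe a selected 19% of trials and average out to 5%. They show how an unlucky trial would mislead and do not show an inflated test.

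**The calculations assume normal complete cases.** With 30% attrition expected, dropout related to outcome can bias either method, and days of use may be skewed. ANCOVA does not cure this.

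**The trial is a pilot and these outcomes are secondary.** This limits the weight of the point. At d = 0.5, power stays below 50% with either method over r = 0.3 to 0.7.

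**Conclusion.** The concern holds as a point to consider, at medium confidence. The plan collects the baseline value of every continuous secondary outcome and names no model that uses it as a covariate. On the change-score reading, the cost is intervals wider than they need be (ANCOVA's would be about 6% to 18% narrower at 14 per arm for r from 0.7 down to 0.3), plus avoidable error in the roughly one trial in five per measure with a baseline imbalance above 0.5 SD.

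The size rests on assumed r, equal SDs, normal scores and ignorable dropout. The gain is negligible near r = 0.9. The planned test remains valid over all randomisations, and the primary threshold outcomes are unaffected.

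**What to change.** In the Statistical Analysis Plan paragraph:

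- For each continuous secondary outcome, make the main estimate the adjusted mean difference with its 95% CI from a linear model of the 4-week score on randomised arm and the baseline score of the same measure.
- If a t-test is kept, label it a descriptive check and state that it is on change.
- State whether DSM-5 OUD criteria will be a symptom count (same model) or a yes/no diagnosis.
- Check the residuals for days of use, which may be skewed.

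The cost is SAP wording and one degree of freedom per model. No new data are needed, because both measurements are already planned in both arms.

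### The SAP's only between-arm analyses are significance tests, with no confidence intervals, on a pilot-sized sample not powered for testing; the difference with its 95% CI should be the main result.

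*Combined protocol and SAP*

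**What the plan says.** The analysis plan is one short paragraph in the section Study Procedures & Statistical Analysis Plan.

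- **Sample size.** It appeals to "best practice guidelines for pilot trial sample size calculations with a medium effect size" and says that "the proposed pilot study will attempt to include a minimum of 15 participants per arm". It then adds: "Accounting for an expected 30% attrition rate, we will attempt to recruit 40 patients".
- **Analysis.** One sentence, which names t-tests and then says that "chi-squared tests will determine mean differences on continuous and dichotomous variables, respectively".
- **Allocation.** Under Procedures, "participants will have an equal chance of being allocated to the PROCare group", which is taken here as 1:1.
- **Outcomes.** Study Aim and Procedures define three primary outcomes, each a rate against a threshold (buprenorphine adherence, care plan adherence, participation in daily surveys). The secondary outcomes are pre/post changes on validated measures, which are also completed at baseline.
- **Purpose.** Procedures says that the pilot "will assess the feasibility, acceptability, and effectiveness of the PROCare Recovery app". Study Aim calls this effectiveness preliminary, and Risks & Benefits uses similar language.

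The document states no alpha, sidedness, power, numerical effect size, analysis population, confidence interval or rule for interpreting a test result.

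**The concern.** The sample size and the analysis serve different purposes. A sample chosen by pilot guidance can be reasonable for estimating a difference and its uncertainty, but the analysis sentence asks for tests. The primary outcomes are rates, so the primary comparison falls to Pearson's chi-squared test. That test returns a p-value and no measure of how large the difference is.

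Two things are at stake. First, with this few patients a real, moderate benefit would usually give p > 0.05, and a reader with only the test result could not tell an ineffective app from an imprecise trial. Second, a result that does reach p < 0.05 will tend to exaggerate the effect, and a later trial planned from it would be too small. The useful product of a pilot this size is an estimate with its interval, and the plan does not require the interval.

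**Working it through.** **Inputs from the Statistical Analysis Plan paragraph:** minimum 15 per arm, 30% attrition, 40 recruited. Allocation is 1:1 (Procedures).

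**Assumed, because the plan is silent:** two-sided alpha 0.05; medium effect meaning d = 0.5 for means and h = 0.5 for rates; control rates of 20% to 50%. The analysis population is also unstated, so three sizes per arm are shown.

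**Step 1. The plan's own figure.** Keeping 30 after 30% loss needs 30 / 0.70 = 42.9, so 43, or 44 with each arm rounded up (15 / 0.70 = 21.4, so 22). The stated 40 is matched only by multiplying up: 15 × 1.30 = 19.5, so 20 per arm. Going forward, 40 × 0.70 = 28, or 14 per arm. This shortfall is a separate matter; here it only explains why both 14 and 15 appear. No power figure is stated, so there is none to reproduce.

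**Step 2. Power of the t-test.** Noncentral t with 2n − 2 degrees of freedom and noncentrality d × √(n/2).

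| n per arm | Noncentrality at d = 0.5 | Power | Missed | d detectable with 80% power |
|---|---|---|---|---|
| 14 (completers of 40) | 1.32 | 24.7% | 75% | 1.10 |
| 15 (stated minimum) | 1.37 | 26.2% | 74% | 1.06 |
| 20 (all randomised) | 1.58 | 33.8% | 66% | 0.91 |

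For scale only, 80% power at d = 0.5 needs 64 completers per arm.

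**Step 3. Power of the chi-squared test, which serves the primary outcomes.** Exact binomial enumeration, no continuity correction, h = 0.5, control rates 20% to 50%: 23% to 26% at 14 per arm, 26% to 28% at 15, and 32% to 36% at 20.

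**Step 4. Sensitivity at 14 per arm, one assumption changed at a time.** d = 0.4: 17.5%. d = 0.6: 33.3%. One-sided 5%: 36.1%. Medium read as w = 0.3 for the chi-squared test: 35.5%. The three more favourable variants still miss the effect about 64% to 67% of the time; d = 0.4 misses it about 82% of the time.

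**Step 5. Exaggeration when significant.** At 14 per arm, p < 0.05 needs an observed standardised difference of at least t(0.975, 26) × √(2/14) = 2.056 × 0.378 = 0.78, which is 0.78 / 0.50 = 1.6 times the assumed true effect. In 200,000 simulated trials with true d = 0.5, significant results overstated the mean difference about 1.9-fold on average.

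**Step 6. Precision if intervals are reported, at 14 per arm.**
- Mean difference, unadjusted: half-width 0.78 SD, the same expression as in Step 5 (0.75 SD at 15 per arm).
- Risk difference at 7/14 against 7/14, Newcombe: the Wilson half-width for one arm is 1.96 / (2 × √(14 + 1.96²)) = 1.96 / (2 × 4.224) = 0.232, and √2 × 0.232 = 0.33.
- The score interval for the same data gives 0.35.
- The Wald formula gives 1.96 × √(2 × 0.25 / 14) = 0.37. It is shown only for comparison, since a score-type interval is what should be used.

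**The case against.** The strongest reply is that this is openly a proof-of-concept pilot and the plan claims less than a critic might suppose. Several stronger readings are tempting, and the documents do not support them.

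- **That the tests decide effectiveness.** The analysis sentence ties them to mean differences only. The link to effectiveness has to be made through Study Aim and Procedures, and Study Aim and Risks & Benefits both use the qualifier preliminary. The unqualified word in Procedures is a matter of editing.
- **That p > 0.05 will be read as no effect.** No such rule is written, and there is no progression criterion. The risk comes from the plan's silence.
- **That the pilot set out to detect a medium effect.** The phrase "pilot trial sample size calculations with a medium effect size" describes the guidance. The title of one cited source refers to minimising the combined size of pilot and main trial, so the medium effect may belong to the later trial. The power figures therefore describe what the tests can do, not a target the plan missed.
- **That 14 per arm and a three-in-four miss rate are facts.** Fourteen requires a completers-only analysis, which is not stated. With all 20 per arm the miss rate is about two in three.

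Two further points stand. Rates and mean differences imply that point estimates will exist, so the firm omission is the interval. And Procedures asks the app group for the daily check-ins, so survey participation may not be an ordinary between-arm comparison with a medium effect.

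The reply does not remove the point. These tests are the only between-arm analysis specified, no interval is requested, and no variant in the working brings power at a medium effect near a usual level. That the trial is a pilot is an argument for estimation.

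**Conclusion.** The point holds in limited form. The plan specifies significance tests alone for a sample justified as a pilot, and tests alone answer the preliminary-effectiveness aim poorly. With two-sided 5% and d = 0.5, both assumed, power is about 25% to 34% depending on whether 14, 15 or 20 per arm are analysed. A medium effect would be missed about two-thirds to three-quarters of the time. The chi-squared tests for the primary rates perform similarly under the assumed control rates.

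A reader might infer that the trial is too small or should not run as designed. That does not follow: the size can be acceptable for estimation, provided that estimation is what the plan asks for.

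**What to change.** In the Statistical Analysis Plan paragraph:

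1. Make the between-arm difference with a 95% CI the main result. For the primary rates, use the risk difference with a score-type interval (Newcombe or score). For the continuous secondary outcomes, use the mean difference adjusted for the baseline value that Procedures already collects.
2. Label p-values exploratory.
3. State the analysis population, and give the expected precision beside the sample size. At 14 per arm this is a half-width of about 0.78 SD before adjustment and about 33 to 35 percentage points for rates near 50%. Baseline adjustment narrows the first to the extent that baseline and follow-up correlate.

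As an editorial matter only, bring the effectiveness wording in Procedures into line with Study Aim.

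The cost is a few sentences and slightly more output, with no change to sample size, data collection or patient procedures. The downside is that the pilot gives no yes/no verdict and its stated precision will look wide.

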### **Specify study eligibility criteria.**

Patients/providers for pilot testing will be recruited through the South Florida Behavioral Health Network, Inc. in Miami, FL. Patients must be  $\geq$  18 years of age, own a smartphone, have a primary DSM-5 (APA, 2013) opioid use disorder (OUD) diagnosis, be receiving buprenorphine as part of their treatment, and no current suicidal ideation or severe mental illness (e.g., schizophrenia).

